7.1.7 Test for Proportion of Subjects with a Characteristic at Visit *t*

In cases that a comparisons between proportions is needed, the Chi-square test will be used to compare the proportions between each of the active treatment arms and the placebo arm. The

Chi-square p-value will be provided for each comparison between the active treatment and the placebo arm. In addition, the difference of in proportions between each active treatment and the placebo arm will be estimated and their corresponding 95% confidence interval will be calculated.

The construction of confidence intervals for binary variables will be based on normal approximation if the number of the events in each individual treatment arm is at least 5. Otherwise, confidence interval using an exact method will be provided. The exact confidence intervals for binary variable within treatment group and between treatment groups will be constructed.

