7.5.2 Secondary and Exploratory Efficacy Analyses

For all secondary endpoints, no multiplicity adjustment will be applied. Nominal p-values will be provided.

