7.5.2.1 Categorical Endpoints

For each of the following categorical secondary endpoints, the estimate and its corresponding two-sided 95% confidence interval will be calculated for the proportion for each treatment arm. In addition, differences of the proportions between each active treatment arm and the placebo arm will be evaluated and their corresponding two-sided 95% confidence intervals and nominal p-values will be provided.

- Proportion of subjects with a ≥ 3 point improvement from baseline in ESSDAI at Week 12
- Proportion of subjects with a ≥ 1 point improvement from baseline in ESSPRI at Week 12
- Proportion of subjects with both ≥ 3 point improvement from baseline in ESSDAI and ≥ 1 point improvement from baseline in ESSPRI at Week 12

The subjects that have discontinued the study prematurely or have missing assessments for ESSDAI or ESSPRI at Week 12, they will be counted in these analyses as having no improvement since baseline.

The same analysis will be repeated at each timepoint of assessment of ESSDAI and ESSPRI as per protocol. For these analyses no nominal p-values will be produced.

For the calculation of ESSDAI refer to [section 8.6](#). For the calculation of ESSPRI refer to [section 0](#).

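### Below 5 events in an arm, the responder CI becomes exact but the p-value stays chi-square, so a Week 12 responder endpoint can show nominal p < 0.05 beside a 95% CI that includes zero

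*SAP*

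**What the plan says.** SAP 7.1.7 prescribes one test whatever the counts: "the Chi-square test will be used to compare the proportions between each of the active treatment arms and the placebo arm". It adds that the "Chi-square p-value will be provided for each comparison between the active treatment and the placebo arm". No small-sample alternative and no continuity correction is mentioned.

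The interval rule does depend on counts. The SAP uses a normal "approximation if the number of the events in each individual treatment arm is at least 5". When that condition fails, "Otherwise, confidence interval using an exact method will be provided". The exact interval covers the difference as well as the single proportions: "The exact confidence intervals for binary variable within treatment group and between treatment groups will be constructed". The method is not named.

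SAP 7.5.2.1 applies this to the three Week 12 responder endpoints (ESSDAI, ESSPRI, and both together). For the between-arm differences, "their corresponding two-sided 95% confidence intervals and nominal p-values will be provided". For subjects who stop early or lack the Week 12 assessment, "they will be counted in these analyses as having no improvement since baseline". P-values are given at Week 12 only. SAP 7.5.2 sets their status: "For all secondary endpoints, no multiplicity adjustment will be applied. Nominal p-values will be provided". Protocol 8.4.2.2 calls the between-arm differences exploratory.

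**The concern.** A reader expects a two-sided p-value below 0.05 and a 95% interval that excludes zero to go together. Here, with few events, the p-value comes from a large-sample test with pooled variance and the interval from an exact procedure, so the two can disagree. The SAP does not say which result governs. Because the exact method is unnamed, whether a given table conflicts may be settled only after unblinding, by a software default or by choice.

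The low-count branch is reachable. There are about 25 subjects per arm, missing outcomes count as non-response, and the combined responder rate cannot exceed that of either component. At stake is a contradictory line in a secondary endpoint table, and room to choose afterwards which half of it to quote.

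**Working it through.** **The plan's own figures.** Protocol 8.1 gives 25 per arm, difference 3, SD 3.2 and two-sided 0.05. The noncentrality is 3 / (3.2 × √(2/25)) = 3.31 on 48 df, so power is 90.1% (stated: about 90%). For 40 per arm and SD 4.8, power is 78.8% (stated: 79%). Both reproduce. The documents give no power or expected response rate for the responder endpoints.

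**Method.** I enumerated all 26 × 26 outcomes for one active arm and placebo with 25 each, reading the 5-event rule as applying to the two arms compared. Chi-square is Pearson's, uncorrected: X² = d² / [p̄(1 − p̄) × 2/25], where d is the difference in proportions and p̄ the pooled rate. The exact unconditional 95% interval inverts two one-sided 0.025 tests. It includes zero, for a table favouring active, when the one-sided p at zero difference, maximised over the common rate, exceeds 0.025. As no method is named, I ran two: tables ordered by the raw difference, and by the score statistic.

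**Worked case, 9/25 v 3/25.** d = 0.36 − 0.12 = 0.24 and p̄ = 12/50 = 0.24.
- X² = 0.0576 / (0.24 × 0.76 × 0.08) = 0.0576 / 0.014592 = 3.947, so p = 0.047.
- Exact one-sided p = 0.027 (score) or 0.059 (raw difference). Both exceed 0.025.
- The raw-difference interval is about −0.055 to 0.505. The score interval has its lower limit only just below zero and its upper limit near 0.470.

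**Other tables at 25 per arm.**

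| Active v placebo | Chi-square p | One-sided exact p, raw | One-sided exact p, score |
|---|---|---|---|
| 6 v 1 | 0.042 | 0.101 | 0.026 |
| 8 v 2 | 0.034 | 0.059 | 0.019 |
| 6 v 0 | 0.009 | 0.059 | 0.005 |

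**Count of conflicts.** 92 tables favour active with chi-square p < 0.05 and an arm below 5 events. The exact interval includes zero in 12 (raw difference) or 2 (score: 9 v 3 and 6 v 1). At the maximum of 40 per arm it is 21 or 2 of 166. With at least 5 events in both arms, no table at 25 or 40 per arm has chi-square p < 0.05 with a normal-approximation interval that includes zero. This form of conflict therefore comes from the switch.

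**Probability at 25 per arm.** The rates are assumptions.

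| Placebo v active | Exact CI used | Conflict, raw | Conflict, score |
|---|---|---|---|
| 10% v 30% | 91% | 27% | 6% |
| 15% v 35% | 69% | 17% | 4% |
| 20% v 40% | 43% | 9.5% | 2% |
| 20% v 30% | 47% | 7.5% | 2% |

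**Size of the chi-square test.** For a common true rate up to 20%, type I error is at most about 0.055 (0.049 at 10%, 0.020 at 5%). The overall maximum, 0.065, occurs at a rate of 50%, where the chance that either arm has fewer than 5 events is about 0.001.

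**The case against.** A reader might infer that the chi-square p-value overstates the evidence when events are few. The size figures do not support that: where the switch operates the test stays close to 0.05, and 0.065 belongs to response rates at which the exact interval is almost never used. Most of the disagreement comes from conservative exact methods. Ten of the 12 raw-difference conflicts disappear under score ordering, and the two that remain miss 0.025 narrowly (0.027 and 0.026). Fisher's 0.095 for 9 v 3 is also from a conservative test and is not the true value. Separate triggers are not in themselves wrong: the 5-event rule suits an interval built on each arm's own variance, whereas chi-square is usually judged on expected counts, which are 6 events per arm for 9 v 3.

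A reader might also infer that low counts will be common. The documents give no response rates. The plan's difference of 3 and SD of 3.2, with normality and an assumed placebo mean change, imply these ESSDAI responder rates:
- placebo change 0: 17% v 50%, an arm below 5 events in 55% of trials, conflict 7% (raw) or 1% (score);
- placebo change −1: 27% v 62%, an arm below 5 in 17%;
- placebo change −2: 38% v 73%, an arm below 5 in 2%.

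These ignore non-responder imputation and do not cover the combined endpoint, where rates would be lower.

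Finally, the p-values are nominal, the SAP sets no significance threshold for these endpoints, and no success claim rests on them. All of this stands and limits the point. It does not remove the unmatched pair or the unnamed method.

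**Conclusion.** The point holds as a minor reporting inconsistency. As written, SAP 7.1.7 can put a nominal p < 0.05 beside a 95% interval that includes zero for a Week 12 responder endpoint. At 25 per arm this affects 12 of 92 low-count tables with chi-square p < 0.05 (raw difference) or 2 of 92 (score). Under assumed rates of 10-20% v 30-40% the probability per comparison is about 7-27% or 2-6%; at higher placebo rates it is close to nil.

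The figures assume an uncorrected chi-square. With a continuity correction, on which the SAP is silent, the conflicts at 25 per arm fall to 4 or 0. Neither materially inflated type I error nor a weakness in the primary analysis follows: the ESSDAI MMRM with Hochberg adjustment is untouched.

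**What to change.** In SAP 7.1.7, name the exact method, for example the exact unconditional score-based interval. State that whenever the exact interval is used, the p-value comes from the test inverted to obtain it and replaces the chi-square p-value. The pair then agrees about zero by construction: for 9 v 3 under the score method, the two-sided p is 2 × 0.0274 = 0.055, in line with an interval that includes zero.

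Swapping in Fisher's test alone is not enough. For 6 v 0, Fisher's p is 0.022 while the raw-difference interval still includes zero, so test and interval must be a matched pair. A different large-sample interval, or a trigger that also counts non-events, is a matter of preference and not needed here.

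The cost is a line or two of SAP wording and slightly larger nominal p-values when events are few (8 v 2: 0.038 instead of 0.034 under the score method). No data, visits or subjects are added.

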7.2 Study Conduct

Relevant protocol deviations, which could have an impact on the primary/key efficacy endpoint, will be identified for all subjects who are randomized and receive study medication during the double-blind period. Details of relevant protocol deviations are provided in [APPENDIX 1](#).

All subjects with relevant protocol deviations that could affect the primary efficacy will be identified prior to database lock and unblinding of treatment assignment. All relevant protocol deviations will be listed and summarized by treatment group. The subjects identified with relevant protocol deviation will not be excluded from any analysis population described in [Section 6.3](#). If at least 10% of total subjects in all treatment arms in the efficacy analysis population demonstrate relevant protocol deviations, a per-protocol analysis may be performed. The per-protocol analysis will exclude data from subjects with relevant protocol deviations as specified in APPENDIX 1.

7.3 Study Population

7.3.1 Subject Disposition

The disposition of subjects will be summarized for the pre-treatment period, double-blind treatment and follow-up periods.

The summary of subject disposition for the pre-treatment period will be based on all enrolled subjects. It will include a summary of the:

- number of subjects enrolled
- number (percentage) of subjects randomized
- number (percentage) of subjects not randomized
- number of subjects randomized and treated by treatment group
- number of subjects randomized but not treated by treatment group
- number (percentage) of subjects per reason for not being randomized.

Percentages will be on all enrolled subjects. The reasons for not being randomized will also be listed, for those subjects that were not randomized.

The summary of subject disposition for the double-blind treatment period will be based on the MITT analysis population and will summarize by treatment group the:

- number (percentage) of subjects completing the double-blind treatment period
- number (percentage) of subjects not completing the double-blind treatment period (i.e. early discontinued subjects)
- number (percentage) of subjects per reason for not completing the double-blind treatment period (i.e. reasons for early discontinuation)
- number (percentage) of subjects continuing in the study (i.e. entering in the follow-up period)
- number (percentage) of subjects not continuing in the study (i.e. not entering in the follow-up period)
- number (percentage) of subjects per reason for not continuing in the study

Percentages will be on all randomized and treated subjects. The reasons for not completing the double-blind treatment period or for not continuing in the study will also be listed, for those subjects that either did not complete the double-blind treatment period or did not continue in the study.

The summary of subject disposition for the follow-up period will be based on the MITT analysis population for those subjects that have entered the follow-up period (based on information on the status page at the end of double-blind treatment) and will summarize by randomized treatment group the:

- number (percentage) of subjects completing the follow-up period
- number (percentage) of subjects not completing the follow-up period
- number (percentage) of subjects per reason for not completing the follow-up period

Percentages will be on all subjects entering the follow-up period. The reasons for not completing the follow-up period will also be listed, for those subjects that did not complete the follow-up period.

The number of subjects enrolled, randomized, and treated will be summarized by country and study site.

7.3.2 Demography and Baseline Characteristics

Demographic and baseline disease characteristics will be summarized by randomized treatment group and overall based on the MITT analysis populations. For continuous variables, they will be summarized using means, standard deviations and ranges, based on non-missing observations (see [Section 7.1.3](#)). The distribution of categorical variables will be summarized by treatment group using frequency and percentage (see [Section 7.1.4](#)). For categorical variables, percentages will be calculated out of the total number of subjects in the data set, overall and by treatment group (i.e., each denominator includes the number of subjects with missing/unknown values for the characteristic).

Table 7.3.2-2: Demographic and Baseline Characteristics

Characteristic	Summarized as	Categories
Age (years)	Categorical and Continuous	< 65yrs ≥ 65yrs
Gender	Categorical	Male Female
Female Age	Categorical	≤ 50yrs > 50yrs
Race	Categorical	White Black or African American Asian Other
Ethnicity (to be summarized only for USA subjects)	Categorical	Hispanic/Latino Non Hispanic/Latino
Region	Categorical	North America South America Europe Asia (see APPENDIX 2)
Total Body Weight (kg)	Continuous	
Time from First Diagnosis of Sjogren’s syndrome (years)	Continuous	
Randomization stratification factors as recorded on IVRS	Categorical	Hydroxychloroquine use (YES/NO) Oral corticosteroid use (YES/NO) Combinations of both: Hydroxychloroquine use and Oral corticosteroid use Hydroxychloroquine use and No oral corticosteroid use No hydroxychloroquine use and Oral corticosteroid use No hydroxychloroquine use and No oral corticosteroid use
Randomization stratification factors as recorded on eCRF	Categorical	Hydroxychloroquine use (YES/NO) Oral corticosteroid use (YES/NO) Combinations of both: Hydroxychloroquine use and Oral corticosteroid use Hydroxychloroquine use and No oral corticosteroid use No hydroxychloroquine use and Oral corticosteroid use No hydroxychloroquine use and No oral corticosteroid use
Number of 2015 ACR-EULAR Classification Criteria met	Continuous	

Table 7.3.2-2: Demographic and Baseline Characteristics

Characteristic	Summarized as	Categories
ESSDAI Total Score	Continuous	
ESSDAI Constitutional Domain Score	Continuous	
ESSDAI Lymphadenopathy Domain Score	Continuous	
ESSDAI Glandular Domain Score	Continuous	
ESSDAI Articular Domain Score	Continuous	
ESSDAI Cutaneous Domain Score	Continuous	
ESSDAI Pulmonary Domain Score	Continuous	
ESSDAI Renal Domain Score	Continuous	
ESSDAI Muscular Domain Score	Continuous	
ESSDAI Peripheral Nervous System (PNS) Domain Score	Continuous	
ESSDAI Central Nervous System (CNS) Domain Score	Continuous	
ESSDAI Haematological Domain Score	Continuous	
ESSDAI Biological Domain Score	Continuous	
ESSPRI	Continuous	
Unstimulated whole saliva secretion	Continuous	
Stimulated whole saliva secretion	Continuous	
Schirmer's Test moisture measure for both eyes	Continuous	
Vaginal dryness numeric rating scale	Continuous	
Physician's global assessment of disease activity (MDGA)	Continuous	
Subject's global assessment of disease activity (PGA)	Continuous	

7.3.3 General Medical History

The number (percent) of subjects with general medical history findings before the first study medication will be summarized by treatment group and overall using the MITT analysis population. A corresponding listing of medical history findings will be provided.

7.3.4 Prior (Current) Medication

Prior (current) medications are defined as medications with a start date prior to the first day of double-blind treatment period and without a stop date prior to the consent date, i.e. current

medication will be any medication with at least 1 dose taken on or after the day of consent date up to the day prior to the first dose of study medication.

Prior medication information before the first study medication will be summarized by drug class and (generic) drug name and by treatment group using relative frequencies. Listings of prior medication will be presented. The results will be based on the MITT analysis population.

Missing and partial date handling of start and stop dates of prior medications, is described in [Section 8.5](#). The World Health Organization (WHO) dictionary is used to code non-study medications.

7.4 Extent of Exposure

7.4.1 Study Therapy

The extent of exposure during the double-blind treatment period will be summarized for the As-treated analysis population in the following ways:

- by the number of days the subject is known to be on study drug, ignoring any dosing interruptions, using the formula below:

$$\text{Exposure (in days)} = (\text{date of last study medication}) - (\text{date of first study medication})$$

For Lulizumab or matching placebo, the date of last study medication corresponds to the last date of study medication + 7 days (the offset of 7 days represents the dosing interval of 7 days).

For BMS-986142 or matching placebo, the date of last study medication corresponds to the last date of study medication +1.

Because subjects receive either lulizumab or BMS-986142 together with the corresponding matching placebo for each medication

- the date/time of first study medication will be the earliest of the dates/times of first administration of BMS-986142 or Lulizumab or matching placebo.
- the date/time of last study medication will be the maximum of last study medication date/time as described above for each medication.

The frequency will be presented according to the duration ranges (in days) : 1-28, 29-56, 57-84 and ≥ 85 .

- by the number of Lulizumab or matching placebo study drug injections. The frequency will be presented using the following ranges in the total number of injections: 1-4, 5-8, 9-12, >12.
- by the number of BMS-986142 or matching placebo doses. The frequency will be presented using the same ranges as for the summary of number of days.

In addition to the frequencies mentioned above, the mean, standard deviation, median, minimum and maximum values will be summarized for all the above mentioned ways of summarizing extend of exposure.

7.4.2 Discontinuations from Study Therapy

Discontinuation from study therapy is defined as subject's termination of the study medication without resumption prior to study completion. Section 3.5 of the protocol mentions the reasons for which a subject must discontinue treatment.

Discontinuation from study therapy during the double-blind period is capture on the study status case report form (CRF) pages. For the analysis of discontinuations from study therapy refer to [section 7.3.1](#).

7.4.3 Treatment Compliance

The CRF for this study will capture information on injections of the Lulizumab or matching placebo and doses of BMS-986142 or matching placebo.

The number of subjects with missed injections or doses (excluding missed injections or doses due to premature discontinuation from the study) will be summarized by number of missed injections or doses based on the As-treated analysis population for the ST period by treatment groups. The summary will be produced separately for missed injections and missed doses. A corresponding listing for all subjects who skip either any injection or dose will be produced.

[REDACTED]

7.4.5 Immunosuppressant Medication

Immunosuppressant medications summaries will be provided to present the medication use of corticosteroids, NSAIDs (non-steroidal anti-inflammatory drugs), and non-biologic DMARDs (non-biologic disease-modifying antirheumatic drugs).

This summary will include both prior and concomitant medications (see [sections 7.3.4](#) and [7.4.4](#) for definitions, respectively).

The number and percent of subjects receiving corticosteroids, NSAIDs, and DMARDs will be summarized by treatment group for MITT analysis population.

7.4.6 Corticosteroids

The average daily corticosteroid dose (prednisone equivalent) and its change from baseline will be summarized over time by treatment group for the double-blind period using the MITT analysis population.

7.4.7 Narcotic analgesics

A summary of use of narcotic analgesics will be provided. This summary will include both prior and concomitant medications (see [sections 7.3.4](#) and [7.4.4](#) for definitions, respectively). The number and percent of subjects receiving narcotic analgesics will be summarized by treatment group for MITT analysis population.

7.4.8 Anticoagulants

A summary of use of anticoagulants will be provided. This summary will include only prior medications (see [sections 7.3.4](#) for definition). The number and percent of subjects receiving anticoagulants as prior medication will be summarized by treatment group for MITT analysis population.

7.5 Efficacy

Unless otherwise specified, all efficacy analyses will be produced using the MITT analysis population.

7.5.1 Primary efficacy analysis

The EULAR Sjögren's Syndrome Disease Activity Index (ESSDAI) is a systemic disease activity index that was designed to measure disease activity in subjects with pSS (see Protocol Appendix 3).³³ The ESSDAI parameters are assessed by the investigators and the results from each assessment are recorded in site source records as well as entered into the corresponding eCRF. The ESSDAI total score will be calculated as described in [section 8.6](#)

The primary efficacy endpoint is change from baseline ESSDAI score at Week 12.

The mixed effects model with repeated measures (MMRM) will be used to model the change from baseline in ESSDAI score over time for all treatment arms. Details of the model are presented in [section 7.1.5.1](#).

The least square means of the differences of Week 12 change in ESSDAI from baseline between each active treatment and the placebo will be estimated and their corresponding two-sided 95% confidence intervals will be provided.

The Hochberg's step-up procedure will be used to adjust the multiplicity due to the comparison of two active treatments (lulizumab or BMS-986142) to the placebo arm. The corresponding adjusted p-values for the Hochberg procedure will be provided.

The model assumption assessment will be performed following the methodology described in [section 7.1.5.2](#).

In addition, the same model will be used to provide estimates for the changes in ESSDAI score at each time point of assessment as per protocol.

In case that more than 10% of subjects in any treatment group have a relevant protocol deviation, leading to exclusion of efficacy data, then this analysis will be repeated excluding efficacy data from subjects with relevant protocol deviations, as described in [APPENDIX 1](#).

